14.5 Ethical Considerations

The study will be conducted in accordance with ethical principles founded in the Declaration of Helsinki. The study must fully adhere to the principles outlined in *Guideline for Good Clinical Practice, ICH Tripartite Guideline, January 1997*, or with local law if it affords greater protection for the patient. The IRB/IEC will review all appropriate study documentation in order to safeguard the rights, safety and well-being of the subjects. The study will only be conducted at sites where IRB/IEC approval has been obtained. The protocol, IB, informed consent form, advertisements (if applicable), written information given to the subjects (including diary cards), safety updates, annual progress reports, and any revisions to these documents will be provided to the IRB/IEC by the investigator or the sponsor, as allowable by local regulations.

14.6 Subject Information and Informed Consent

After the study has been fully explained, written informed consent will be obtained from either the subject or his/her guardian or legal representative prior to study participation. The method of obtaining and documenting the informed consent and the contents of the consent is to comply with ICH-GCP and all applicable regulatory requirement(s).

14.7 Subject Confidentiality

In order to maintain subject privacy, all eCRFs, study drug accountability records, study reports and communications will identify the subject by initials where permitted and/or by the assigned subject number. The subject's confidentiality will be maintained and will not be made publicly available to the extent permitted by the applicable laws and regulations.

14.8 Investigator Compliance

The investigator will conduct the trial in compliance with the protocol provided by Plexxikon, and given approval/favorable opinion by the IRB/IEC and the appropriate regulatory authority(ies). Modifications to the protocol are not be made without agreement of both the investigator and Plexxikon. Changes to the protocol will require written IRB/IEC approval/favorable opinion prior to implementation, except when the modification is needed to eliminate an immediate hazard(s) to subjects. Plexxikon, or a CRO designee, will submit all

protocol modifications to the appropriate regulatory authority(ies) in accordance with the governing regulations.

When immediate deviation from the protocol is required to eliminate an immediate hazard(s) to subjects, the investigator will contact Plexxikon, or a CRO designee, if circumstances permit, to discuss the planned course of action. Any departures from the protocol must be documented.

14.9 On-site Audits

Regulatory authorities, the IEC/IRB, and/or Plexxikon may request access to all source documents, eCRFs, and other study documentation for on-site audit or inspection. Direct access to these documents must be guaranteed by the investigator, who must provide support at all times for these activities.

14.10 Investigator and Site Responsibility for Drug Accountability

Accountability for the study drug at the trial site is the responsibility of the investigator. Drug accountability records indicating the drug's delivery date to the site, inventory at the site, use by each subject, and amount returned to Plexxikon, or a CRO designee, (or disposal of the drug, if approved by Plexxikon) will be maintained by the clinical site. Plexxikon or its CRO designee will review drug accountability at the site on an ongoing basis.

All material containing study drug will be treated and disposed of as hazardous waste in accordance with governing regulations.

14.11 Product Complaints

A product complaint is any dissatisfaction with a product that may be attributed to the identity, quality, durability, reliability, or safety of the product. Individuals who identify a potential product complaint situation should immediately report the event. Whenever possible, the associated product should be maintained in accordance with the label instructions pending further guidance from a Plexxikon quality representative.

For Product Complaints, refer to the Study Pharmacy Manual for instructions and details.

14.12 Closure of the Study

The study will be considered closed after the last subject has progressed, died, withdrawn from study treatment, or been lost to follow-up, whichever occurs first.

The Sponsor currently has no plans to provide PLX9486 or the combination of PLX9486 + PLX3397 to study subjects after the close of the study or earlier subject withdrawal. However, the Sponsor will evaluate the appropriateness of continuing to provide PLX9486 or the combination of PLX9486 + PLX3397 to study subjects after evaluating study data pertaining to the primary efficacy outcome measure and safety. These analyses may be conducted prior to study completion. For subjects who are demonstrating a clinical benefit at the end of this trial, the possibility of continuing their treatment in this or a roll-over protocol may be considered.

Within 90 days of the end of the study the sponsor will notify the competent authorities and the IECs in all member states where the study is being carried out that the study has ended.

Within 1 year of the end of the study, a summary of the clinical trial results will be submitted to the competent authorities and IECs in all member states involved in the study.

Study participation by individual sites or the entire study may be prematurely terminated, if in the opinion of the investigator or Plexxikon, there is sufficient reasonable cause. Written notification documenting the reason for study termination will be provided to the investigator or Plexxikon by the terminating party.

Circumstances that may warrant termination include, but are not limited to:

- Determination of unexpected, significant, or unacceptable risk to subjects
- Failure to enter subjects at an acceptable rate
- Insufficient adherence to protocol requirements
- Insufficient, incomplete, and/or un-evaluable data
- Determination of efficacy based on interim analysis
- Plans to modify, suspend or discontinue the development of the study drug

Should the study be closed prematurely, the site will no longer be able to access the EDC application, will not have a right to use the EDC application, and will cease using the password or access materials once their participation in the study has concluded. In the event that any access devices for the EDC application have been provided, these will be returned to Plexxikon once the site's participation in the study has concluded.

Within 15 days of premature closure, Plexxikon must notify the competent authorities and IECs of any member state where the study is being conducted, providing the reasons for study closure.

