6.2 Part 2 (Extension Cohorts) Objectives

The primary objectives for Part 2 of this study are:

- [REDACTED]
- **Part 2b.** Assess the safety and tolerability of the combination of PLX9486 and PLX3397 and to establish an RP2D of PLX9486 in combination with PLX3397 in patients with advanced solid tumors (including GIST).
- [REDACTED]
- [REDACTED]
- **Part 2e.** Assess the safety and tolerability of the combination of PLX9486 and sunitinib and to establish an RP2D of PLX9486 in combination with sunitinib in patients with advanced solid tumors (including GIST).
- [REDACTED]

The secondary objectives for Part 2 are:

- To determine the pharmacokinetics (PK) of PLX9486 as a single agent and in combination with PLX3397 or sunitinib.
- [REDACTED]
- To estimate the following:
 - ORR (using RECIST 1.1)
 - CBR (Parts 2b and e)
 - Overall survival (OS) and 12-month OS rate
 - Progression-free survival (PFS) and 6-month PFS rate

- Duration of response (DoR)

The exploratory objectives are:

- To assess biomarkers in peripheral blood and in archival tumor tissue
- To assess tumor response in the Part 2 cohorts by Choi criteria ([Choi 2007](#))

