7.3 Duration of Study

Screening Period:

- 21 days (with the exception of tumor burden assessment (i.e., CT scan), which may be performed within 28 days of dosing

Treatment Period:

- **Part 1 and Part 2 (a-f).** 28-day (± 7 days) cycles until patient discontinuation or withdrawal or study termination (see [Section 10.4](#))

Follow-up Period:

An end of study visit must occur ≥ 30 days after the last dose of PLX9486 and prior to starting any new anti-cancer therapy. A post-study follow-up contact by phone by site staff will be conducted every 3 months during Year 1, then every 6 months thereafter to obtain information on any new anti-cancer therapy received, response, and survival status.

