11.0 STUDY ASSESSMENTS

Event schedules are summarized in [Table 1](#) (Part 1), [Table 2](#) [REDACTED] [Table 3](#) (Part 2b), [Table 4](#) [REDACTED] [Table 5](#) [REDACTED] [Table 6](#) (Part 2e), and [Table 7](#) [REDACTED]

All patients must provide written informed consent. During the consent process, the person obtaining consent must inform the patient of all elements of the study. No protocol-specific procedures, including Screening procedures, are to be performed until the patient has signed and dated an institutional review board (IRB)/independent ethics committee (IEC)-approved informed consent form. The study begins with the signing and dating of the informed consent form.

A patient will be considered enrolled in the study once all inclusion and exclusion criteria have been met, and the completed patient enrollment form has been submitted to Plexxikon Inc., signed by the appropriate representative, and returned to the investigative site.

Screening procedures are to be performed within 21 days before Cycle 1 Day 1 of study therapy. Each treatment cycle for Part 1, [REDACTED] 2b, [REDACTED] 2e, and [REDACTED] will be 28 days.

Dose interruptions in the middle of a treatment cycle will not affect the cycle and day count on the schedule of assessments. For example, if study drug is held on Cycle 1 Day 10, the following day should still be called Cycle 1 Day 11, etc. If a dose interruption occurs at the beginning of a new cycle, then the new cycle and day count will begin when study drug is restarted. For example, if study drug is held at the Cycle 2 Day 1 visit, then the day that the patient does resume dosing will be called Cycle 2 Day 1.

The end of the study for each patient is defined as the date of the last dose of PLX9486, PLX3397, or sunitinib (see [Section 10.4](#) for reasons for discontinuation or withdrawal of a patient from the study).

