13.3 Monitoring of Adverse Events and Period of Observation

All AEs will be recorded from the time the consent is signed through 30 days after last dose of study drug or prior to initiating new anticancer therapy, whichever occurs first. AEs that occur after signing informed consent but before first dose of study drug that are not related to a protocol-mandated procedure will be recorded as medical history only. AEs occurring as a result of a protocol-mandated procedure after signing of informed consent will be recorded as AEs.

All SAEs will be evaluated from the time the consent is signed through 30 days after last dose of study and prior to starting any new anticancer therapy. Any SAE occurring within this window must be reported to Plexxikon or its designee within 24 hours of the knowledge of the event.

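### The closure rule (14.12) and the per-patient end of study (11.0) fall before the end-of-study visit, the 30-day AE/SAE window and the survival contacts that the protocol also requires

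*Protocol*

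**What the plan says.** Protocol section 14.12 considers the study "closed after the last subject has progressed, died, withdrawn from study treatment, or been lost to follow-up, whichever occurs first". Section 11.0 adds a per-patient rule: "The end of the study for each patient is defined as the date of the last dose of PLX9486, PLX3397, or sunitinib".

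Other sections schedule activity after those points:

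- Section 7.3, visit: "An end of study visit must occur ≥ 30 days after the last dose of PLX9486 and prior to starting any new anti-cancer therapy".
- Section 7.3, phone contacts: "conducted every 3 months during Year 1, then every 6 months thereafter to obtain information on any new anti-cancer therapy received, response, and survival status". No last contact is defined.
- Section 13.3, adverse events: "All AEs will be recorded from the time the consent is signed through 30 days after last dose of study drug", or until new anticancer therapy if that is sooner. For serious events: "All SAEs will be evaluated from the time the consent is signed through 30 days after last dose of study". Section 13.2 sets a matching window for SAEs and deaths.
- Section 6.2 lists "Overall survival (OS) and 12-month OS rate" among the secondary objectives of Part 2.

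Section 10.4 places the end-of-study procedures no later than 30 days after drug is stopped, whereas 7.3 asks for them no earlier than 30 days after the last dose.

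**The concern.** A closure definition should come after the last thing the protocol requires. Here the first of four events in the last subject closes the study, and two of them, progression and stopping drug, come before required follow-up. Survival contacts have no end date of their own, so closure is the only rule in the document that could end them. That matters because overall survival and the 12-month rate depend on those contacts.

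Progression is a doubtful closure event for a second reason. Sections 9.4.2 and 9.5 let a patient with slowly or locally progressive disease resume or continue study drug after radiation or a local procedure, and 14.12 does not define progression so as to exclude such cases. Read literally, closure could be reached while someone is still being dosed.

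At stake are the last subjects' post-treatment safety window, the length of survival follow-up, and a definite date from which the 90-day notification and one-year results summary in 14.12 can run.

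**Working it through.** The plan gives no figure to reproduce, so the check is a timeline followed by a sensitivity calculation.

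**Timeline for the last subject.** Take day 0 as the date this subject stops drug, which triggers closure under 14.12 and end of study under 11.0. Months are 30.44 days. Survival contacts are counted from the last dose, an assumption because 7.3 gives no start point for Year 1.

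| Requirement | Source | Day |
|---|---|---|
| Study closed | 14.12 | 0 |
| Patient's end of study | 11.0 | 0 |
| AE/SAE window ends | 13.2, 13.3 | 30, or earlier if new therapy starts |
| End-of-study visit | 7.3 | 30 or later |
| Survival contacts | 7.3 | about 91, 183, 274, 365, 548, 730, ... |

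Every later row falls after closure. If the trigger is this subject's death or loss to follow-up, nothing is lost for that subject. The 7.3 and 10.4 timings for the end-of-study procedures agree only if they fall exactly on day 30.

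**Distance to the 12-month landmark.** If the last subject stops after c cycles of 28 days, closure precedes that subject's 12-month point by 365 − 28c days:

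- c = 1: 365 − 28 = 337
- c = 2: 365 − 56 = 309
- c = 4: 365 − 112 = 253
- c = 6: 365 − 168 = 197
- c = 12: 365 − 336 = 29
- c = 13: 365 − 364 = 1

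**How many patients this touches.** Let patient i enter at E_i, uniform over an accrual period A, and stay on treatment for T_i, exponential with median 6.2 months (rate ln 2 / 6.2 = 0.112 per month). Closure is C = max(E_i + T_i), and the quantity of interest is the mean share of patients with C − E_i < 12 months. The 6.2 months is the historical median PFS on sunitinib in section 5.1, used only as a stand-in for time on treatment. The values of n and A and the exponential form are assumptions. Results from 20,000 runs per setting:

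| n | A (months) | Share under 12 months' potential follow-up |
|---|---|---|
| 12 | 12 to 18 | 3.7% to 4.5% |
| 15 | 12 to 18 | about 2% to 3% |
| 30 | 12 to 18 | 0.1% to 0.3% |
| 25 | 12 to 30 | 0.3% to 1.2% |

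The n = 25 row is the most relevant, because closure is study-wide: the synopsis reports 49 patients treated and section 5.5.1.1 reports 24 in Part 1, so 49 − 24 = 25 in Part 2. The upper value there is 1.2% × 25 = 0.3 of a patient on average.

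**The case against.** A reader might infer that the protocol's own rule cuts off survival and late safety data. The documents do not support that. No section orders collection to stop at closure. The phone contacts are labelled post-study, so they are meant to run after a patient's study has ended, which fits 11.0. Section 10.4 says that follow-up information will be obtained after discontinuation and that all patients are to be followed for safety where possible. The AE and SAE duties run from the last dose, not from closure. Loss of access to the data-capture system is stated only for premature closure.

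A reader might also infer that patients would be left without drug. Section 14.12 allows continued treatment, in this or a roll-over protocol, to be considered for those who benefit. The Part 1 roll-over in 7.1 is a weak example, since the synopsis says only Part 2b and 2e patients are now treated.

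Nor do the documents support a claim of serious damage to overall survival. It is a secondary, descriptive endpoint, Kaplan-Meier estimation handles administrative censoring, and 12 months is the only survival landmark the protocol names.

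These points stand, and they limit the harm. They do not remove the conflict: to do what 7.3 and 13.3 require for the last subject, the sponsor must keep collecting data in a study that 14.12 already calls closed. The survival contacts still have no stated end, and the 9.4.2 and 9.5 routes to treatment after progression remain open to current patients.

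**Conclusion.** Sections 14.12 and 11.0 contradict 7.3, 13.2 and 13.3, and the contradiction is worth removing because doing so is cheap. Its size is modest. The safety gap concerns mainly the last subject or subjects, for up to 30 days each, and does not arise when death or loss to follow-up is the trigger. The 12-month survival rate is little affected, with about 0% to 5% of patients short of 12 months' potential follow-up across the settings tried and about 1% or less at n of about 25. Those percentages rest on uniform accrual, exponential time on treatment and a borrowed median. The contradiction itself rests on the text alone.

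**What to change.** In 14.12, define closure as the later of:

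- (a) the last subject's end-of-study visit and the end of the 30-day AE/SAE window after the last dose of any study drug; and
- (b) a stated survival cut-off, for example the date when every Part 2 patient has died, been lost to follow-up, withdrawn consent, or reached at least 12 months from Cycle 1 Day 1.

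Remove progression and withdrawal from treatment as closure events. In 11.0, call the last-dose date end of treatment and tie end of study to the cut-off in (b). Do not tie it to the last survival contact, because 7.3 sets no last contact. Reconcile the timing of the end-of-study procedures in 10.4 with 7.3.

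The cost is a wording amendment and a longer open period, using contacts already scheduled. If the last patient to enter stops after two cycles, the study stays open about 10 months longer (309 / 30.44 = 10.2). After one cycle it would be about 11 (337 / 30.44 = 11.1), and after 13 cycles almost nothing for survival. No dosing or treatment rule changes.

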14.13 Record Retention

The investigator will maintain all study records according to ICH-GCP and applicable regulatory requirement(s). Records will be retained for at least 2 years after the last marketing application approval or 2 years after formal discontinuation of the clinical development of the investigational product or according to applicable regulatory requirement(s). If the investigator withdraws from the responsibility of keeping the study records, custody must be transferred to a person willing to accept the responsibility and Plexxikon notified.

15.0 USE OF INFORMATION

All information regarding PLX9486 and PLX3397 supplied by Plexxikon to the investigator is privileged and confidential information. The investigator agrees to use this information to accomplish the study and will not use it for other purposes without consent from Plexxikon. It is understood that there is an obligation to provide Plexxikon with complete data obtained during the study. The information obtained from the clinical study will be used towards the

development of PLX9486 and PLX3397 and may be disclosed to regulatory authority(ies), other investigators, corporate partners, or consultants as required.

Upon completion of the clinical study and evaluation of results by Plexxikon, the hospital or institution and/or investigator may publish or disclose the clinical trial results pursuant to the terms contained in the applicable Clinical Trial Agreement (CTA).

ATTACHMENT 1: LABORATORY TESTS**Hematology**

- Hemoglobin and hematocrit
- White blood cell count with differential
- Platelet count
- RBC Count

Blood Chemistry

• Sodium	• Glucose	• Total and direct bilirubin
• Potassium	• Blood urea nitrogen	• Aspartate aminotransferase (AST)
• Chloride	• Creatinine	• Alanine aminotransferase (ALT)
• CO2	• Uric acid	• Alkaline phosphatase (AP)
• Calcium	• Total protein	• Lactate dehydrogenase (LDH)
• Magnesium	• Albumin	
• Phosphorus		

Coagulation Tests

Prothrombin time (PT)/International normalized ratio (INR)

Partial thromboplastin time (PTT)

Urinalysis (microscopic)

• pH	• Nitrites
• Protein/albumin	• Ketones/acetone
• Glucose/sugar	• Hemoglobin/blood
• WBCs	• Casts or other microscopic findings

Serum Pregnancy Test (β -HCG): women of child-bearing potential

Plasma Samples for PK

Blood Response Biomarkers (Tumor DNA)

Paired Biopsy Tissue Response Biomarkers

RNA sequencing

Tumor DNA sequencing/Tumor Gene Expression Analysis

Other response or resistance biomarkers as appropriate

Because the identification of new response prediction or early response biomarkers of disease activity is a rapidly developing field, the definitive list of analyses remains to be determined, and may include additional markers of macrophage activity, in addition to anti-tumor biomarkers that may be related to PLX9486 treatment.

ATTACHMENT 2: STRONG CYP3A4 INHIBITORS AND INDUCERS AND CYP3A4 SUBSRATES

Strong Inhibitors	Strong Inducers	Substrates
indinavir	carbamazepine	Alfuzosin
nelfinavir	efavirenz	Alprazolam
ritonavir	nevirapine	Budesonide
clarithromycin	phenobarbital	Carbamazepine
itraconazole	phenytoin	Colchicine
ketoconazole	pioglitazone	Cyclosporine
nefazodone	rifabutin	Dexamethasone
erythromycin		Disopyramide
grapefruit juice		Ergotamine
verapamil		Fluticasone
suboxone		Lovastatin
diltiazem		Methylprednisolone
		Midazolam
		Pimozide
		Quinidine
		Repaglinide
		Rifabutin
		Sildenafil
		Simvastatin
		Tadalafil
		Triazolam
		Vardenafil
		Vinblastine
		Vincristine

Source: [IUPUI Division of Clinical Pharmacology, The Flockhart Table: P450 Drug Interaction Table, 2016](#)

**ATTACHMENT 3: DRUGS CLEARLY ASSOCIATED WITH THE RISK OF
TORSADES DE POINTES (TDP) AND QT PROLONGATION**

Anti-arrhythmics
 
 - Amiodarone - Disopyramide - Dofetilide - Dronedarone - Flecainide - Ibutilide - Procainamide (Oral off US mkt) - Quinidine - Sotalol - Ritonavir - Indinavir - Nelfinavir 
Antimicrobials
 
 - Azithromycin - Ciprofloxacin - Clarithromycin - Erythromycin - Grepafloxacin (Off market worldwide) - Levofloxacin - Moxifloxacin - Sparfloxacin (Removed from US Market) - Pentamidine - Fluconazole 
Anti-psychotics
 
 - Haloperidol - Mesoridazine (Removed from US Market) - Pimozide - Thioridazine - Chlorpromazine - Droperidol - Sulpiride (On non US Market) 	
Anti-cancers
 
 - Arsenic trioxide - Vandetanib 
Anti-depressants, SSRIs
 
 - Citalopram - Escitalopram 
Antihistamines
 
 - Astemizole (Removed from US Market) - Terfenadine (Removed from US Market) 
Anti-malarials
 
 - Chloroquine - Halofantrine 
Antilipemic
 
 - Probucol (Removed from US Market) - Ondansetron 
Opiates
 
 - Levomethadyl acetate (Removed from US Market) - Methadone 
Anesthetics, general
 
 - Propofol - Sevoflurane 
Others
 
 - Cisapride (Removed from US Market) - Cocaine - Anagrelide - Bepridil (Removed from US Market) - Domperidone (On non US Market)
---	---

